9.3 Data review

The CRA will periodically monitor the source data to guarantee the consistency with that recorded in the eCRF. The medical monitors will review eCRF data from the medical perspective, and data manage personnel will check the integrity and logicality of eCRF data.

In terms of problems found during the data review, relevant personnel will create data queries to sites in the EDC system, and personnel at site will answer the queries and make necessary changes to the data. All records of data revision and relevant operations are trailed in the EDC system.

9.4 Database locking and archiving

After all study data are collected cleaned and locking conditions are reached through data review, database will be locked. Locked data will be sent to statistical analysts for analysis.

After the completion of the study, patient eCRF in PDF form shall be generated from EDC and saved on CD-ROM which will be submitted to the sponsor and each site. Study documents shall be archived and managed in accordance with the requirements addressed in GCP.

9.5 Database management and quality control

For studies using eCRFs, Haihe personnel (or designated CRO) will review the data entered by investigational staff for consistency, completeness and accuracy. Electronic data queries stating the nature of the problem and requesting clarification will be created for discrepancies and missing values and sent to the investigational site via the EDC system. Designated investigator site staff are required to respond promptly to queries and to make any necessary changes to the data.

Concomitant treatments and prior medications entered into the database will be coded using the WHO Drug Reference List, which employs the Anatomical Therapeutic Chemical classification

system. Medical history/current medical conditions and adverse events will be coded using the Medical dictionary for regulatory activities (MedDRA) terminology.

Samples and/or data will be processed centrally and the results will be sent electronically to Haihe (or a designated CRO).

10 Statistical methods and data analysis

This section describes the statistical methods and data presentations to be used in the summary and analysis of safety, tolerability, pharmacodynamics (PD), pharmacokinetics (PK), and preliminary efficacy data for the study drug. Background information is provided for the overall study design and objectives. The reader is referred to the previous sections on this protocol for details of study conduct and data collection.

Unless otherwise specified, ‘Phase I’ in this section is referred to as the dose-finding phase of the study, in which the BOPIN design is used to assess the MTD and/or RP2D of the study drug. ‘Phase II’ is referred to as the extension phase where the preliminary efficacy is evaluated for each selected patient cohorts.

10.1 Study Endpoints

Study endpoints see [Section 3](#).

10.2 Analysis sets

10.2.1 All-Treated Set

The All-treated set includes all patients who have received at least one dose of study medication. This set will be used for efficacy analysis.

10.2.2 Safety Set

The Safety Set (SS) includes all patients who receive at least one dose of study medication. This set will be used for safety analysis.

10.2.3 Pharmacokinetic analysis set

The pharmacokinetic analysis set (PKS) consists of all patients who receive at least 1 dose of study drug and have sufficient, valid PK samples to estimate key parameters for at least 1 of the days of sampling.

10.2.4 Pharmacodynamics analysis set

The pharmacodynamics analysis set (PDS) consists of all patients set who receive at least 1 dose of study drug and have sufficient, valid PD samples to estimate key parameters for at least 1 of the days of sampling.

10.3 Covariates and Subgroups

No covariates will be accounted for in Phase I (dose-finding). In Phase II (cohort extension), analyses will be stratified by tumor types and/or genetic mutations in order to evaluate the preliminary efficacy. Patient to the request of the sponsor, any further analyses could be conducted based on any additional covariates/subgroups. The details of these analyses will be described in the statistical analysis plan (SAP).

10.4 Sample Size Considerations

Phase I Dose Escalation Stage

The planned maximum sample size in Phase I dose escalation stage (ATD + BOIN) is 58 including up to 40 subjects for ATD + QD dose escalation cohorts (Part A) and up to 18 subjects for the additional BID dose escalation cohorts (Part B). During the ATD, one-patient per cohort is required for dose escalation. Once the BOIN design starts, cohorts of 3 patients will be used for dose escalation and the maximum number of patients for each dose level should not exceed 15 patients and 12 patients for BOIN design Part A and Part B, respectively.

Phase I Dose Expansion Stage

We plan to recruit up to 15 patients per expansion cohort in the phase I stage of the study. The enrolled patients with different cancers must have confirmation of specific MAPK pathway genetic alteration. The primary focus of the dose expansion is to further assess the safety and pharmacokinetics of HH2710. Preliminary efficacy will also be examined but serve only for an exploratory purpose.

Phase II Dose Extension Stage

In Phase II, patients will be recruited into the following 4 cohorts at the RP2D level:

Cohort 1: Patients with *BRAF/NRAS* (mutation sites as follows: *NRAS* G13V, *NRAS* Q61, *BRAF* V600, *BRAF* G469A, L485W, L597Q, T599dup) mutated melanoma;

Cohort 2: Patients with *BRAF/NRAS* (mutation sites as follows: *NRAS* G13V, *NRAS* Q61, *BRAF* V600, *BRAF* G469A, L485W, L597Q, T599dup) mutated non-small cell lung cancer;

Cohort 3: Patients with *BRAF* V600 mutated Langerhans Cell Histiocytosis Syndrome (LCH)/ Erdheim-Chester disease (ECD);

Cohort 4: Patients with *RAS/RAF/MEK/ERK* mutated tumors that are not included in other cohorts.

The sample size in Cohort 1 and Cohort 2 is justified according to the Bayesian optimal phase 2 (BOP2) design [60]. Specifically, let n denote the interim sample size and N denote the maximum sample size. Let p_{eff} denote the probability of efficacy (response rate) and define the null hypothesis $H_0: p_{eff} \leq 0.05$, representing that the treatment is inefficacious. We will stop enrolling patients and claim that the treatment is not promising if

$$Pr(p_{eff} > 0.05 | data) < \lambda \left(\frac{n}{N}\right)^\alpha,$$

where $\lambda=0.75$ and $\alpha=0.2$ are design parameters optimized to minimize the chance of incorrectly claiming that an efficacious treatment is not promising (i.e., type II error) under the alternative hypothesis $H_1: p_{eff} = 0.16$, while controlling the type I error rate at 0.1 (i.e., the chance of incorrectly claiming that an inefficacious treatment is promising is no more than 10%). Assuming a Beta (0.05,0.95) prior distribution for p_{eff} , the above decision rule corresponds to the following stopping boundaries and yields a statistical power of 0.8201 under H_1 :

Table 10-1 Optimized stopping boundaries for cohort 1 and cohort 2 in Phase II

# patients treated	Stop if # responses <=
23	1
36	3

Based on [Table 10-1](#), we will perform an interim analysis for the first 23 patients. When at least 2 patients experience CR or PR or SD ($SD \geq 6$ month) events, the study will continue recruiting up to 13 more patients in the second stage. When the total number of patients reaches the maximum sample size of 36, we reject the null hypothesis and conclude that the treatment is promising if the number of responses is greater than 3; otherwise we conclude that the treatment is not promising.

We plan to recruit a maximum of 9 patients in Cohort 3. Since there are currently no sufficient data available (due to the rarity of the disease), we are unable to calculate the sample size provided for an acceptable statistical justification. However, at this stage, we think that data from 9 patients is considered to be adequate to allow a preliminary investigation of the study objectives for this cohort [60].

Cohort 4 will include a maximum of 27 patients. Patients included in this cohort will have different cancer types led by different genetic mutations. Thus, it is difficult to calculate sample size for this cohort based on very accurate efficacy goals (e.g. minimum ORR for the alternative hypothesis). Therefore, this cohort serves for an exploratory purpose and the number of patients has been based on the desire to obtain adequate data whilst exposing as few patients as possible to the study procedures.

10.5 Planned Analyses

10.5.1 Interim Analyses

There are three planned interim analyses during the study. One is performed for the determination of RP2D when Phase I completes. The other two are conducted for futility evaluation for the first 23 patients in each of cohort 1 and cohort 2 when they have recruited and completed the assessment in Phase II. Any additional interim analyses can be conducted as requested by the sponsor for safety/efficacy monitoring while the study is ongoing.

A sponsor-led data review committee will be used to evaluate safety as well as preliminary efficacy during the study. In Phase I, safety data will be reviewed by the committee after a minimum of 3 patients have been enrolled into each dose level and received treatment. Once the dose escalation stage completes, the committee will review safety data as well as data from other sources (e.g. efficacy, PK/PD) to determine the RP2D for Phase II.

In Phase II, the efficacy review will be conducted for cohort 1 and cohort 2 by the committee when each cohort has recruited and completed the assessment for the first 23 patients. For safety, the committee will review the data when every 6 or 12 patients have recruited and received treatments in all cohorts. Following the data review, the committee will decide as to whether the cohort may continue, whether amendment(s) to the protocol should be implemented, or whether the study should be stopped.

Members of the committee will be internal to the sponsor, which can include employees and study investigators.

Any outcomes of these safety and efficacy reviews that affect study conduct will be communicated in a timely manner to the investigators for notification of the Institutional Review Boards/Ethics Committees (IRBs/ECs).

10.5.2 Primary Analysis

The primary analyses in Phase I focuses on safety endpoints for HH2710 administered alone in patients with the advanced and/or refractory tumors. The RP2D will be determined based upon the observed DLTs and information from other sources (e.g. pharmacokinetics) as described in the protocol.

In Phase II, the primary analyses will investigate the preliminary efficacy of the ORR and other endpoints including DoR, DCR, TTR, TTP, PFS and 1-year OS rate for each tumor type and each genetic mutation.

10.5.3 Final Analysis

The intended purpose of the final analysis is to provide the up-to-date information on the primary/secondary endpoints after patients have completed the follow-ups as described in the

protocol. The methods used in the final analyses will be similar as those used in the primary analyses.

10.6 Planned Methods of Analysis

10.6.1 General Considerations

The analysis methods used in the study will be mainly descriptive statistics.

Unless stated otherwise, the term “descriptive statistics” refers to the number of patients (n), mean, median, standard deviation (SD), minimum (min), and maximum (max) for continuous data and frequencies and percentages for categorical data. Min and max values will be rounded to the precision of the original value, means and medians will be rounded to 1 decimal place greater than the precision of the original value, and SDs will be rounded to 2 decimal places greater than the precision of the original value. Percentages will be rounded to the nearest whole number (zeroes are not displayed) with values of “< 1%” and “> 99%” shown as necessary for values falling near the boundaries.

Unless otherwise noted, all data collected during the study will be included in data listings and will be sorted by study (Phase I or Phase II), patient number, and then by date/time for each patient number. For Phase I expansion and phase II, patients will additionally be sorted by tumor types and genetic mutations.

Demographic and baseline characteristic data will be summarized with descriptive statistics by treatment group and overall for each study part using the All-treated and SS populations. The variables include, but not limited to, age (years), gender, race, weight (kg), height (cm), ECOG performance status, tumor type, genetic mutation, previous chemotherapy and previous immunotherapy.

All analyses will be conducted using SAS® version 9.2 or higher.

10.6.2 Primary Efficacy Endpoint

In Phase I, there is no primary efficacy endpoints.

In Phase II, the objective response rate (ORR) will be calculated and summarized for each tumor type and genetic mutation. If possible, a 95% of confidence interval should be provided for each ORR.

10.6.3 Secondary Efficacy Endpoint(s)

In Phase I, there is no secondary efficacy endpoints.

In Phase II, Kaplan-Meier method will be used to analyze the duration of response (DOR), the progression-free survival (PFS), time to response (TTR), time to progression (TTP) and 1-year overall survival (OS) rate for each tumor type and genetic mutation. If possible, a 95% of

confidence interval should be provided for each estimate. The point estimate and its 95% exact confidence interval (Clopper Pearson) will be used for analyzing DCR.

10.6.4 Pharmacokinetic Analysis

Samples for PK analysis of HH2710 and its metabolite will be obtained from all patients enrolled in Phase I dose escalation/expansion and Phase II trial.

Below is the list of PK parameters that will be calculated after single dose (C1D1) and steady State (C1D15).

Table 10-2 PK Parameters Description

PK Parameter (plasma)	Description
C _{max}	Peak plasma concentration determined manually by visual inspection of plasma concentration vs. time figures on the untransformed (linear) scale of measurement
t _{max}	Time to reach the peak plasma concentration determined manually by visual inspection of plasma concentration vs. time figures on the untransformed (linear) scale of measurement
AUC ₀₋₂₄	Area under the plasma concentration-time curve from 0 to 24 hours post-dose, calculated by linear/log trapezoidal method
AUC _{0-∞}	Area under the plasma concentration-time curve from time zero to infinity after dosing calculated by linear/log trapezoidal method
%AUC _{extrap}	Area under the plasma concentration-time curve extrapolated from time t to infinity as a percentage of total AUC (%)
Lambda _z (λ _z)	Terminal phase rate constant, determined by linear regression of at least 3 points on the terminal phase of the log-linear plasma concentration-time curve. The correlation coefficient (r ²) for the goodness of the fit of the regression line through the data points has to be 0.85 or higher for the value to be considered reliable. If the WinNonlin data points are not on the linear portion of the terminal slope, the data points will be selected manually prior to calculation of Lambda _z
t _{1/2}	Terminal half-life, defined as 0.693 (ln2) divided by Lambda z
CL/F	The apparent total body clearance of drug from the plasma (volume x time-1)
V _z /F	The apparent volume of distribution during terminal phase (associated with λ _z)(volume)

Descriptive statistics [n, arithmetic mean, standard deviation, coefficient of variation (CV), median, minimum, maximum, geometric mean, geometric standard deviation geometric CV] will be used

to summarize PK parameters by treatment. For $t_{1/2}$ and t_{max} , regular descriptive statistics and 95% confidence intervals about the arithmetic mean will be calculated, if possible, for each dose. Refer to the PK analysis plan for additional details regarding with the PK analyses.

A listing of blood PK concentrations and parameters will be provided.

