6.1.1 Dosing regimen

The dosing and treatment schedule, as shown in the below.

Table 6-1 Proposed Dose and treatment schedule of Phase I

Bayesian optimal interval (BOIN) design incorporated with an accelerated titration Schedule of HH2710				
Dose Level	Dose of HH2710	Patient	Pharmaceutical form and route of administration	Frequency and/or Regimen
Level 1	25mg	3	Capsules for oral use	QD at C1D1, then BID from C1D2 (21 days/cycle)
Level 2	50mg	3	Capsules for oral use	BID (21 days/cycle)
Level 3	100mg	3+N [#]	Capsules for oral use	BID (21 days/cycle)
Level 4	300mg	3+N [#]	Capsules for oral use	QD (21 days/cycle)
Level 5	400mg (Total daily dose*)	3+N	Capsules for oral use	QD/BID (21 days/cycle)
Level 6	600mg (Total daily dose*)	3+N	Capsules for oral use	QD/BID (21 days/cycle)

Level 7	800mg (Total daily dose*)	3+N	Capsules for oral use	QD/BID (21 days/cycle)
#: The number of pts enrolled in each dose is specified by the BOPIN rules;				
*: Proposed daily dose is the total dose each day with QD or BID dose frequency.				
Dosing frequency and dose level may be adjusted on the basis of available pharmacokinetic data and safety.				

Table 6-2 Dose and treatment schedule of Phase II

Dose extension Schedule of HH2710			
Dose Level	Dose of HH2710	Pharmaceutical form and route of administration	Frequency and/or Regimen
1	RP2D	Capsules for oral use	QD or BID (21 days/cycle)

In Phase I, the first 3 patients will be administered orally (in the fasted state) HH2710 capsule once daily (QD) at the first day, then sampling for PK, from the second day, HH2710 capsule will be administered orally on a continuous twice daily (BID) schedule, on a flat scale of mg/day and not individually adjusted by weight or body surface area. The fourth and later patients will be administered with HH2710 capsule twice daily (BID) from the first day of cycle 1, patients will be instructed to take their study medication 12±2 hour interval. Based on human PK data, from the fourth dose level, the patients will be administered with HH2710 capsule once daily (QD). The Investigator must instruct the patient to take the study drug exactly as prescribed.

- Except on days of single dose PK sampling, patients should take HH2710 capsule follow the doctor's advice at approximately the same time each day starting at Cycle 1 Day 1, Patient should not eat until 2 hours after HH2710 administration.

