1. The local report of MAPK pathway gene status must be documented in the source files at the site, if enrollment eligible patient's MAPK pathway gene status has been determined by local laboratory testing. For phase Ib/II, Each enrollment eligible patient must provide adequate archival and/or freshly FFPE tumor samples, which will be used for a MAPK pathway gene status determination at a Sponsor Designated Central Laboratory.

2. Full medical history at screening, review/update of history only at subsequent visits.
3. Serum pregnancy test is mandatory at screening visit. After screening and baseline, urine pregnancy test which if positive, confirm with serum test. Whereas serum pregnancy test is required at EOT visit. Note that procedures performed during screening within 3 days prior to dosing do not need to be repeated on C1D1.
4. After screening and baseline, urine pregnancy test which if positive, confirm with serum test.
5. Study drug to be taken QD at cycle1 day 1, and study drug to be taken twice daily (BID) from second day of cycle 1 only in the first 3 patients. The fourth and later patients will be administered with HH2710 capsule twice daily (BID) from the first day of cycle 1. From the fourth dose level. The patients will be administered with HH2710 capsule once daily (QD) orBID. The investigator should instruct the patient when dispensing the drug. Vital sign exam is detected at pre-dose, and 2h, 4h, after dose in C1D1, and C1D15, and be detected pre-dose in other setting time points.
6. On C1D1 and C1D15, vital sign exam should be detected at pre-dose, 2h after dose, and 4h after dose. At other time points, the vital signs exam can be detected at pre-dose.
7. If the Screening results within 7 days before C1D1 are judged to be normal by the investigator, C1D1 may be waived.
8. If the Screening results within 28 days before C1D1 are judged to be normal by the investigator, C1D1 may be waived.
9. Dense pharmacokinetic sampling will be done in the dose escalation portion of the trial. Sparse pharmacokinetic sampling will be done every two cycles prior to Day 1 dosing in all patients in the dose escalation between Cycle 1 (not included) to Cycle 9 (including Cycle 9)(Cycle 3 Day 1, Cycle 5 Day 1, Cycle 7 Day 1 , Cycle 9 Day 1).A pre-dose sample is included in Table 7-3 for patients in the dose escalation portion of the trial.

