Refer to the [HH2710-G101 Laboratory Manual] for detailed instructions for the collection, handling, and shipment of PK samples.

Intensive PK sampling will be done in the dose escalation portion of the trial. Additional PK sampling will be drawn every two cycles prior to Day 1 dosing in all patients in the dose escalation between Cycle 1 to Cycle 9 (e.g. Cycle 3 Day 1, Cycle 5 Day 1, Cycle 7 Day 1, Cycle 9 Day 1) ([Table 7-2](#)).

PK samples at pre-dose, 2h, 4h, a 6h, 8h, and 24h post dose will also be obtained at Cycle 1 Day 1 and Cycle 1 Day 15 for patients in the Phase I dose expansion stage and Phase II portions of the trial ([Table 7-3](#)).

Table 7-2: PK blood sampling time for Phase I dose escalation stage

CxDx	C1D1	C1D1	C1D1	C1D1	C1D1	C1D1	C1D1	C1D1	C1D1	C1D2	C1D7	C1D10	C1D15	C1D15	
No.	1	2	3	4	5	6	7	8	9	10	11	12	13	14	15
Time	pre-dose	15min	30min	1h	2h	3h	4h	6h	8h	12h (If available)	24h (pre-dose)	pre-dose	pre-dose	pre-dose	15min
Window (min)	-30	±5	±5	±5	±10	±10	±10	±30	±30	±60	-30	-30	-30	-30	±5
Blood Sampling	2mL	2mL	2mL	2mL	2mL	2mL	2mL	2mL	2mL	2mL	2mL	2mL	2mL	2mL	2mL
CxDx	C1D15	C1D15	C1D15	C1D15	C1D15	C1D15	C1D15	C1D15	C1D16	C2D1	C3D1	C5D1	C7D1	C9D1	NA
No.	16	17	18	19	20	21	22	23	24	25	26	27	28	29	NA
Time	30min	1h	2h	3h	4h	6h	8h	12h (If available)	pre-dose	pre-dose	pre-dose	pre-dose	pre-dose	pre-dose	NA
Window(min)	±5	±5	±10	±10	±10	±30	±30	±60	-30	-30	-30	-30	-30	-30	NA

Blood Sampling	2mL	NA											
----------------	-----	-----	-----	-----	-----	-----	-----	-----	-----	-----	-----	-----	----

Table 7-3: PK blood sampling time for Phase I dose expansion stage and Phase II

CxDx	C1D1	C1D1	C1D1	C1D1	C1D1	C1D2	C1D15	C1D15	C1D15	C1D15	C1D15	C1D15
No.	1	2	3	4	5	6	7	8	9	10	11	12
Time	pre-dose	2h	4h	6h	8h	24h	pre-dose	2h	4h	6h	8h	24h
Window(min)	-30	±10	±10	±30	±30	±60	-30	±10	±10	±30	±30	±60
Blood Sampling	2mL	2mL	2mL	2mL	2mL	2mL	2mL	2mL	2mL	2mL	2mL	2mL

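### For patients who take two doses on Cycle 1 Day 1, the 24 h sample follows the second dose, so the protocol's single-dose AUC0-24 cannot be observed and the SAP's AUC0-last may carry the same error

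*Protocol*

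**What the plan says.** **Dosing on Day 1.** Protocol Section 6.1.1 gives Level 1 (25 mg, three patients) the regimen "QD at C1D1, then BID from C1D2 (21 days/cycle"), so that single-dose PK can be sampled. The exception ends there: "The fourth and later patients will be administered with HH2710 capsule twice daily (BID) from the first day of cycle 1", with doses at a "12±2 hour interval". The footnotes to Table 7-1 agree: "study drug to be taken twice daily (BID) from second day of cycle 1 only in the first 3 patients". From the fourth dose level the protocol allows QD or BID. No section withholds the second Day 1 dose for PK purposes.

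**Sampling.** Table 7-2 ("PK blood sampling time for Phase I dose escalation stage") runs to 8 h on C1D1. It then has a 12 h draw only if available (window ±60 min, not tied to the second dose) and a C1D2 pre-dose sample labelled 24 h. Table 7-3 (expansion and Phase II) has pre-dose, 2, 4, 6, 8 and 24 h and no 12 h draw. Neither schedule samples the peak after a second dose.

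**Analysis.** Protocol Section 10.6.4 introduces Table 10-2 as the "PK parameters that will be calculated after single dose (C1D1) and steady State (C1D15"), and so treats C1D1 as a single dose for all patients. It defines AUC0-24 as "Area under the plasma concentration-time curve from 0 to 24 hours post-dose, calculated by linear/log trapezoidal method" and also lists AUC0-inf, percent extrapolated, terminal slope, half-life, CL/F and Vz/F. The slope needs at least three terminal points and r2 of 0.85 or more, and points may be chosen manually. Further detail is left to a PK analysis plan. SAP Section 8.9, Table 2, lists AUC0-12 and AUC0-last in place of AUC0-24 and AUC0-inf, with no rule by regimen. SAP Section 8.12 does not record this as a change from the protocol.

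**The concern.** A 24 h AUC is a single-dose quantity only if one dose was given in those 24 hours. For a patient dosed twice on Day 1, the trapezoid from the last daytime sample to the 24 h sample joins a point before the second dose to a point that includes it, and misses the second peak. The result is too large for one dose and too small for two. Nothing in Table 10-2 screens it out, because the r2 rule protects only the terminal slope.

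PK parameters are the Phase I secondary endpoint (Table 3-1, where the AUC is given as AUC0-t). They also feed the choice of dosing frequency and of the RP2D (Sections 2.3 and 6.2.4). A biased Day 1 AUC for BID cohorts would distort comparison with QD cohorts and any accumulation ratio built on it.

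**Working it through.** The plan states no figure to reproduce. The check is who is affected, then how far the AUC moves.

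**Patients affected.** Protocol Section 4.1 reports BID escalation patients to 18 Jan 2022 as 25 mg n=3, 50 mg n=3 and 100 mg n=4, so 10 in all. The 25 mg patients had a true single dose on C1D1, which leaves 3 + 4 = 7. Part B adds up to about 18. BID expansion or Phase II patients would also be affected.

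**Inputs.** Half-life 8.42 and 10.9 h (Protocol Section 4.1); sampling times from Tables 7-2 and 7-3; second equal dose at 12 h. The documents give no human absorption rate, so ka = 0.5, 1 and 2 per hour is an assumption.

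**Model.** With k = ln 2 / half-life, one dose gives, up to a scale factor,

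c(t) = ka/(ka − k) × [exp(−kt) − exp(−ka·t)].

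Two doses give c(t) + c(t − 12) after 12 h. AUC uses linear/log trapezoids on the scheduled samples, as in Table 10-2.

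**One case in full** (half-life 8.42 h, ka = 1; k = 0.0823):
- c(8) = 0.564, c(12) = 0.406, c(24) = 0.151.
- The observed 24 h value after two doses is 0.151 + 0.406 = 0.557. That is 0.557/0.151 = 3.69 times the single-dose value and 0.557/0.564 = 0.99 of the 8 h value.
- True AUC0-24 is 10.31 for one dose and 17.53 for two.
- Table 7-2 samples without the 12 h draw give 14.22: 14.22/10.31 = 1.38 and 14.22/17.53 = 0.81.
- With the 12 h draw taken before the second dose they give 12.95: ratios 1.26 and 0.74.

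**All cases, second dose at 12 h**

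| Quantity | Range |
|---|---|
| 24 h concentration / single-dose value | 3.1-3.7 |
| 24 h concentration / 8 h concentration | 0.99-1.17 |
| AUC0-24 / true single-dose AUC0-24 | 1.24-1.41 |
| AUC0-24 / true two-dose AUC0-24 | 0.72-0.86 |
| r2 of last-three-point slope including 24 h | 0.06-0.62 |

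**Moving the second dose within 12±2 h.** If it is taken at 10 h and the 12 h draw follows it, AUC0-24 is 1.64-1.81 times the single-dose value. It then happens to fall near the two-dose value (0.96-1.01). Over second-dose times of 10 to 14 h, r2 of slopes through the 24 h point reaches at most 0.81, still below 0.85.

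**Leaving the 24 h sample out**

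| Last usable sample | Half-life, true 8.42 h | Half-life, true 10.9 h | AUC0-inf extrapolated |
|---|---|---|---|
| 12 h, before second dose | 8.4-9.9 h | 10.9-13.2 h | 39-58% |
| 8 h, ka 1-2 | 8.4-9.1 h | 10.9-12.0 h | 54-68% |
| 8 h, ka 0.5 | 17.7 h | 29.7 h | 77-86% |

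The slope-based parameters can therefore be estimated, but weakly when sampling stops at 8 h. In the slow-absorption case the 17.7 h estimate has r2 = 0.93 and would pass the protocol's rule, which is why the extrapolated fraction needs to be shown.

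**The case against.** The strongest reply is that the plan already contains safeguards. A terminal slope through the contaminated point fails r2 ≥ 0.85 in every scenario, manual point selection is allowed, and no section says the 24 h point must enter the slope. The SAP already lists AUC0-12, a PK analysis plan not supplied here may settle the rest, the PK summaries are descriptive, and SAP Section 7 says the programme has stopped and many analyses may not be done.

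Much of this stands, and it rules out several stronger readings:

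- **That every C1D1 parameter is wrong for BID patients.** The first three patients and the QD cohorts have valid single-dose profiles. For the others, slope, half-life, AUC0-inf and CL/F go wrong only if the 24 h point is used.
- **That a half-life above 100 h would be reported.** The model can produce one, but it would be flagged as unreliable. The figure also depends on a second dose at exactly 12 h: at 10 h the 6, 8 and 24 h fit can give 52-73 h when the true value is 8.42 h.
- **That C1D1 half-life and CL/F should be barred for BID patients.** With a 12 h sample before the second dose they are recoverable, as shown above.
- **That this explains the reported 3-4 fold accumulation.** With linear kinetics, 1/(1 − exp(−k × interval)) gives 1.16-1.28 (QD) or 1.59-1.87 (BID) at the stated half-lives, so the figures do not agree. Nothing in the documents links that gap to this sample.

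The reply does not rescue AUC0-24. The r2 rule does not apply to it, and the SAP's AUC0-last takes in the second dose if 24 h counts as the last observation. A PK analysis plan could correct this, but Table 10-2 as written is still wrong for these patients. The early stop lowers the number affected; the SAP still plans the PK summaries and listings.

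**Conclusion.** The point holds in a limited form. For patients given two doses on C1D1, a single-dose AUC0-24 cannot be observed under either sampling schedule. Computed as written with the second dose at 12 h, it overstates the single-dose value by about 24-41% and falls 14-28% short of the two-dose value. This is a stated analysis that returns a wrong number, not only a missing detail. The SAP's AUC0-last has the same weakness unless the last observation is defined to precede the second dose.

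That the sample follows a second dose comes straight from the dosing and sampling sections and needs no model. The size rests on a noise-free one-compartment model with an assumed absorption rate and shifts with the actual time of the second dose. The change is worth making but bears on descriptive PK only: no formal decision rule uses a C1D1 AUC.

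**What to change.** Add to Protocol Section 10.6.4, SAP Section 8.9 and the PK analysis plan, for patients given two doses on C1D1:

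1. Exclude the Day 2 (24 h) sample from all C1D1 single-dose derivations: AUC, terminal slope and everything based on the slope. Do not report C1D1 AUC0-24.
2. Report Cmax, tmax and AUC0-12 where a 12 h sample was drawn before the second dose, checked against recorded dosing and sampling times. Otherwise report AUC0-8, which is all that Table 7-3 supports.
3. Report slope-based parameters only from samples before the second dose, subject to the r2 rule and with the percent of AUC extrapolated shown beside them.
4. Define AUC0-last so that the last observation precedes the second dose.

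Keep the full parameter set for the first three patients and the QD cohorts. Reconcile Protocol Table 10-2 with SAP Table 2: AUC0-24 and AUC0-inf against AUC0-12 and AUC0-last, and steady state at C1D15 against Day 22, for which Table 7-2 has only a pre-dose sample (C2D1). Record the outcome in SAP Section 8.12.

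The cost is wording, with no new samples. The price is fewer or less precise single-dose parameters for BID cohorts, and an AUC over a shorter interval that is not directly comparable with AUC0-24 in the QD cohorts.
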